### **(iii)Methods**

This project includes **FOUR parts** – Part I randomized control trial, Part II longitudinal quantitative study (i.e., prospective cohort study), Part III longitudinal qualitative study, and Part IV longitudinal workplace hygiene study.

### *(iii.1) Procedure of Part I study*

**Part I** is a 9-month **randomized controlled trial** to be conducted with single blinding and concealment during Year 1-2 (as shown in **Figure 1**).

**Study subjects of the RCT:** Two hundred ninety four workers from non-office, mobile and office work settings will be invited to participate in the RCT. The aim of the RCT is to test the hypothesis that a 9-month intervention program improves primarily the attitude towards vaccination and COVID-19 testing, with impact on the improving the actual uptake of COVID-19 testing and risk profile toward outbreaks at workplace.

**Procedures of the RCT:** All 294 participants will be randomized to intervention group and control group. Intervention group will receive theory-based educational intervention using the Theory of Planned Behaviours (TPB) PLUS general health information, while the control group will receive only general health information. As this RCT will investigate factors that can explain worker's intention to vaccination and virus testing, the theoretical framework using the theory for planned behavior (i.e., TPB) is a proper approach for improving workers' attitude toward SARS-CoV-2 and raise their intention to vaccination and virus testing. The intervention will be implemented at the baseline with measurements repeated at the 3rd month, 6th month and 9th month. The standardized mode of intervention includes face-to-face/online seminar (depends on the COVID-19 situation), message via mobile phone, promotion pamphlet, etc.

Primary outcomes of the RCT include attitude to vaccination and virus testing, and the secondary outcomes of the RCT are actual uptakes of virus antibody testing and changes of risk profile toward outbreaks in the workplace.

Key contents of intervention would include:

- TPB intervention: building positive attitudes towards COVID-19 related preventive behaviour (e.g., good compliance with infection control measures, encouraging uptake of testing and vaccination), subjective norms (tackling strategies for perceived social pressure from others or normative beliefs), and improving perceived behavioural control towards risks of outbreaks in workplace.
- Other necessary information: basic knowledge of SARS-CoV-2, chain of infection, health and social consequences of infection, general infection control measures, workplace engineering and administrative control measures.

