**Sample size:** We estimated sample size for the Part I – Randomized controlled trial according to two independent proportions power analysis. As there is no relevant data of willingness to vaccination on our target subjects to guide the sample size calculation regarding an educational intervention against COVID-19, we employed a conservative assumption that the intervention will make a 20% change for worker's attitude to vaccination/virus test, sample size for both groups/arms will be 124, 130, 124, 109 and 79 for the proportion of willingness to vaccination/virus test of 30%, 40%, 50%, 60%, and 70%, respectively, with a 90% G-power. Therefore, a minimal 79 pairs subjects are required to achieve the primary objective (RCT) of this proposal project; if further assuming a loss-to-follow-up rate of about 40%, then an overall 222 participants with 111 subjects in the intervention group and 111 subjects in the control group are required. However, if given the most conservative sample size estimation with 40% loss-to-

follow-up rate, a total of 364 subjects with 182 subjects in each arm of RCT ( $130*1.4$ ) are required. Therefore, the overall sample size for RCT could reasonably range from 222 to 364 to satisfy the primary research objective of this proposal project. In the proposed RCT, we considered taking the mean of the “most-least conservative” sample sizes of 294 [ $(222+364)/2$ ] from G-power as a reasonable sample size with 147 subjects in each arm, and this sample size (i.e., 294) has already taken into consideration a potential loss-to-follow-up rate of about 40%.

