### **(iv) Data processing & analysis**

For quantitative results, descriptive analysis and Chi-square will be used for baseline data to analyse the difference in exposure and prevention, willingness to vaccination/testing and actual uptake of tests between comparison groups (e.g., work settings). Paired t-test and covariance analysis will be performed to compare the longitudinal changes of scores of each exposure prevention behaviour factors, attitude and willingness to vaccination and virus testing over time. Structural equation modelling and multivariate regression logistic modelling will be used to analyze the structural relationship between measured variables and latent constructs, as well as examine the association of exposure profile with willingness to vaccination/testing or uptake testing. Effectiveness of intervention will be examined by multivariable linear (for continuous nature of outcome) or Cox proportional hazard models (for binary outcome). Loss-to-follow-up will be reported and intention-to-treat analysis will be used for addressing the loss-to-follow-

up issue of the RCT. All statistical analyses for longitudinal quantitative and RCT data will be conducted by SPSS Version 26 and/or SAS 9.4 (SAS Institute Inc., North Carolina). P-value of less than 0.05 is considered statistically significant.

For qualitative analysis, the tape-recorded individual interviews will be transcribed verbatim and thematically analysed using Grounded Theory approach. Data will be horizontally compared between participants, and longitudinally analysed, tracking and explaining attitudinal and behavioral changes of individuals across time. The qualitative data will be delineated to a typology of reasons for (1) accepting, delaying or refusal of COVID-19 vaccine, and (2) factors contributing to uptake of COVID-19 testing in the workplace, generated through thematic analysis.

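### The RCT intervention includes a group seminar, but the sample size and models treat participants as independent; if outcomes correlate within sessions, standard errors are too small and type I error exceeds 5%

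*Combined protocol and SAP*

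**What the plan says.** Section (iii.1) makes the individual worker the unit of randomisation: "All 294 participants will be randomized to intervention group and control group". It describes delivery as follows: "The standardized mode of intervention includes face-to-face/online seminar", with the choice between the two left to the state of the epidemic, together with mobile-phone messages, a pamphlet and similar material. For the comparator it says only that "the control group will receive only general health information", without saying whether this is given to groups or to individuals.

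Section (ii), under Sample size, bases the RCT on a "two independent proportions power analysis". For the analysis, section (iv) states: "Effectiveness of intervention will be examined by multivariable linear (for continuous nature of outcome) or Cox proportional hazard models (for binary outcome"). The decision rule there is "P-value of less than 0.05 is considered statistically significant", and the RCT is to be analysed by intention to treat.

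No section gives the size or number of seminars, an ICC, a session term in a model, or a variance estimate that allows for grouping.

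**The concern.** A seminar, in person or online, is a group mode of delivery. Individual randomisation makes the arms comparable at baseline, but it does not prevent correlation that arises afterwards because people attend the same session. Sessions can differ in how they run and in how the audience responds. The primary outcomes are attitudes, which a shared session could plausibly move together.

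If that happens, the intervention arm holds less independent information than its head count suggests. A model that assumes independence then understates the standard error of the arm difference. Confidence intervals are too narrow, whether or not the intervention works, and the 5% rule rejects too often when the average effect is zero. Both primary outcomes, attitude to vaccination and attitude to virus testing, would be affected.

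**Working it through.** **1. The plan's own figure.** Section (ii) gives 124, 130, 124, 109 and 79 per arm before loss, for willingness of 30, 40, 50, 60 and 70%, a 20-point change and 90% power. The pooled two-proportion formula, two-sided 5%, for 40 v 60% gives

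n = [1.96·√(2·0.5·0.5) + 1.2816·√(0.4·0.6 + 0.6·0.4)]² / 0.20² = 5.170 / 0.04 = 129.3, so 130.

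The same formula gives 124, 130, 124, 109 and 82. The first four match exactly, and the stated 79 matches the unpooled and arcsine versions. The plan's figures therefore reproduce under independence, with no design effect.

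**2. Inputs for the clustering check.**
- From the documents: 147 per arm, about 40% loss, 5% level.
- Assumed, because the documents do not give them: m = 10 to 30 people per session, ICC = 0.01 to 0.05, and sessions in the intervention arm only.

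**3. Formulas.**
- Intervention-arm design effect: DE = 1 + (m − 1)·ICC. Control arm: 1.
- Variance inflation of the difference, equal arms: V = (DE + 1)/2.
- True standard error divided by model standard error: √V.
- Actual type I error: 2·[1 − Φ(1.96/√V)].

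**4. Results.**

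| m | ICC | DE | V | √V | Type I error |
|---|---|---|---|---|---|
| any | 0 | 1.00 | 1.000 | 1.000 | 5.0% |
| 10 | 0.01 | 1.09 | 1.045 | 1.022 | 5.5% |
| 20 | 0.02 | 1.38 | 1.190 | 1.091 | 7.2% |
| 30 | 0.05 | 2.45 | 1.725 | 1.313 | 13.6% |

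The model standard error is too small by 1 − 1/√V, or 2% to 24%. Equivalently, a correct interval is √V − 1 wider, or 2% to 31%.

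**5. With the planned loss.** If only completers contribute outcomes, 40% loss turns 10, 20 and 30 per session into 6, 12 and 18:

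| m analysed | ICC | DE | V | Type I error |
|---|---|---|---|---|
| 6 | 0.01 | 1.05 | 1.025 | 5.3% |
| 12 | 0.02 | 1.22 | 1.110 | 6.3% |
| 18 | 0.05 | 1.85 | 1.425 | 10.1% |

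**6. Simulation check.** Beta-binomial outcomes, 147 per arm, m = 20, 40,000 runs per setting: 5.3% at ICC 0, 6.5% at 0.01 and 11.1% at 0.05. The formula gives 5.0%, 6.1% and 10.7%. The two agree closely; the simple z-test itself rejects slightly above 5% at ICC 0. The formula is for a difference in means or proportions and is only a guide for the Cox model.

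**7. Cost in sample size.** Multiplying 130 per arm by V at m = 20 gives 130 × 1.095 = 142.4, so 143 (ICC 0.01), or 130 × 1.475 = 191.8, so 192 (ICC 0.05).

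**The case against.** The strongest reply is that the inflation is conditional at every step.

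- **No ICC or session size is given.** With an ICC near 0, or with small groups, the error stays close to 5%. This stands, and the figures above are a range under stated assumptions.
- **The seminar is one of several modes.** Messages and a pamphlet can reach people individually and may dilute a session effect. This stands as a reason to expect a lower ICC, but it does not show that the ICC is zero.
- **Shared presenters and group discussion are not described.** This stands. If one presenter ran every session, the presenter would add no variation between sessions. Subjective norms appear in section (iii.1) as intervention content, which is not evidence that norms form within a session.
- **If the seminar affected nobody, grouping after individual randomisation would not itself inflate the error.** Correct. The type I statement applies to a zero average effect with real session-to-session variation. Interval coverage suffers whenever sessions vary.
- **Control delivery is not stated.** A reader might infer that controls are ungrouped, but section (iii.1) does not say so. If controls also met in groups, the same inputs would give a larger error (16.1% instead of 10.7% at m = 20, ICC 0.05), and a model treating controls as singletons would be wrong.
- **Covariates in the multivariable models could lower the residual ICC.** Possible, though section (iv) names none for the RCT.

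**Conclusion.** The omission is real: a group component is planned, and neither the sample size nor the analysis allows for correlation within sessions. The direction is also clear, since a positive correlation makes the planned standard errors too small.

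The size rests on assumptions. With 10 to 30 per session, ICC 0.01 to 0.05 and grouping in the intervention arm only, type I error would be about 5.5% to 13.6%, or about 5.3% to 10.1% with 6 to 18 analysed per session. It would be close to 5% if the ICC is near 0.

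A reader might go further and infer that this trial's type I error does exceed 5%, or that the whole intervention is delivered in seminars. The documents support neither: they give no ICC or session size, and they list other modes of delivery. The point is worth acting on because the allowance is cheap and session membership may be hard to reconstruct later.

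**What to change.** - **State** the planned seminar size and number, and how the control arm receives its information.
- **Record** the assigned seminar session for every intervention participant, and for controls if they are also grouped. Use the assigned session, not the one attended: attendance is post-randomisation and non-attenders would have no session. Under intention to treat they stay in their assigned session.
- **Analyse** both primary outcomes with a partially nested model: a session random effect (or a frailty term in the Cox model) in the grouped arm, ungrouped controls as singletons, and a small-sample degrees-of-freedom correction. Small-sample-corrected cluster-robust standard errors are an alternative. If controls are grouped, model their sessions too.
- **Plan** several smaller sessions instead of one or a few large ones where this costs nothing. At 30 per session, 147 participants make about five sessions (147/30 = 4.9), from which a session variance is unstable even with correction. From a single session it cannot be estimated at all.

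The cost is one recorded variable and one model term. The downside is confidence intervals about 2% to 31% wider under the assumptions above, and lower power. For 40 v 60% with 88 analysed per arm (147 × 0.6), power is 76% without clustering. By the same normal approximation it falls to 75% (m = 6, ICC 0.01) or 61% (m = 18, ICC 0.05), before any loss from the degrees-of-freedom correction.

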### **(ii) Subjects to be included**

**Study subjects:** In the Part I randomized controlled trial (RCT), 294 eligible workers from 3 non-healthcare work settings will be recruited, and randomized into intervention group (147 subjects) and control group (147 subjects). To be eligible to the Part I RCT, all participants are required to be aged 18 or above, who can read Chinese and currently being employed in three non-healthcare work settings from non-office, mobile, and office work environment in Hong Kong. We attempt to follow-up all participants of the RCT for 9 months to observe the effectiveness of the intervention on improving the primary outcomes, i.e., attitude to vaccination and SARS-CoV-2 testing.

In Part II longitudinal quantitative study, we plan to recruit a total of 1,495 workers who are aged 18 or above and currently working in non-office, mobile, or office work setting in Hong Kong. All eligible study subjects in Part II longitudinal/ prospective cohort study will be recruited in the timeline of 1.5th -3.5th year of the project and followed up for 2 years to observe the changes of attitude to vaccination and virus testing as well as risk profiles of workers towards outbreaks over time.

Figure 1. Workflow chart of hazard identification of outbreaks and control measures in work settings

\* After considering a lost-to-follow-up rate of about 40%

In the Part III longitudinal qualitative study, we plan to recruit an overall 26 management staff and frontline workers (in a ratio of 1:2) with same inclusion/exclusion criteria as the Part I & II study, i.e., aged 18 or above and currently being employed in three non-healthcare work settings from non-office, mobile, and office work environment in Hong Kong.

All above planned number of participants to be enrolled in the baseline of the Part I, II and III study have already considered a potential loss-to-follow-up rate of about 40%.

**Settings:** The 3 work settings are categorized by types as below according to their job nature and working environment:

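### The RCT names two primary outcomes but has no success rule or error control across them, and its 90% power does not survive the planned loss to follow-up

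*Combined protocol and SAP*

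**What the plan says.** All references are to the combined protocol and SAP.

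- **Outcomes.** Section (iii.1): "Primary outcomes of the RCT include attitude to vaccination and virus testing". Section (ii) also uses the plural: "improving the primary outcomes, i.e., attitude to vaccination and SARS-CoV-2 testing".
- **Hypothesis.** Section (iii.1) sets out to test that "a 9-month intervention program improves primarily the attitude towards vaccination and COVID-19 testing". Measurements are at baseline and months 3, 6 and 9.
- **Sizing.** Section (ii), Sample size, assumes "the intervention will make a 20% change for worker's attitude to vaccination/virus test". With 90% power it gives 124, 130, 124, 109 and 79 per arm for willingness proportions of 30, 40, 50, 60 and 70%. The smallest and largest sizes, multiplied by 1.4, become totals of 222 and 364. The trial takes their mean, as 294 (147 per arm), and says that "this sample size (i.e., 294) has already taken into consideration a potential loss-to-follow-up rate of about 40" per cent.
- **Threshold.** Section (iv): "P-value of less than 0.05 is considered statistically significant". No alpha split, testing order or success rule appears anywhere.
- **Model.** Section (iv): "Effectiveness of intervention will be examined by multivariable linear (for continuous nature of outcome) or Cox proportional hazard models (for binary outcome"). The same section plans paired t-tests and covariance analysis of attitude and willingness scores. It names intention-to-treat but no method for missing values.

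**The concern.** Two primary outcomes, each tested at 0.05, need a rule for what counts as success. If a positive result on either is enough, the chance of at least one false primary claim exceeds 5%. If both must be positive, the error rate holds and the cost falls on power, which the sizing does not address. With no rule written down, the choice can be made after the results are known.

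Two further matters bear on the same primary claim. First, the sizing treats attitude as a proportion while the analysis section refers to scores, so the primary test is not fixed. Second, the 90% power behind the sizing does not hold for the number of participants that the plan expects to keep.

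**Working it through.** **Step 1. Reproduce the plan's sizes.** Inputs from section (ii): a 20-point absolute increase and 90% power. Two-sided 0.05 is my assumption, because sidedness is not stated; one-sided versions do not reproduce the series. Pooled formula, with p̄ the mean of p1 and p2:

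n = [1.960·√(2p̄(1−p̄)) + 1.282·√(p1(1−p1)+p2(1−p2))]² / (p2−p1)²

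For 40% to 60%: (1.386 + 0.888)² / 0.04 ≈ 129.3, so 130. The five results are 124, 130, 124, 109 and 82. The first four match the printed values. The printed 79 agrees with either the unpooled or the arcsine formula. These are sizes for one comparison, with no allowance for a second outcome.

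**Step 2. Error if either outcome may be claimed.** The documents give no correlation between the two test statistics, so 0, 0.5 and 0.8 are assumptions.

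- Correlation 0: 1 − 0.95² = 9.75%
- Correlation 0.5 (bivariate normal integration): 9.1%
- Correlation 0.8: 7.8%

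If both are required, the chance of falsely claiming trial success is at most 5%.

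**Step 3. Evaluable numbers per arm.**

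- 147/1.4 = 105 (the plan's own arithmetic, reversed)
- 147 × 0.6 = 88 (a literal 40% loss)
- 147 (upper bound, nobody lost)

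The 105 is already below the printed 124, 130, 124 and 109.

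**Step 4. Single-outcome power** for a binary outcome, +20 points, two-sided 0.05:

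power = Φ{[0.20·√n − 1.960·√(2p̄(1−p̄))] / √(p1(1−p1)+p2(1−p2))}

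For 40% to 60% with n = 105: (2.049 − 1.386)/0.693 = 0.958, and Φ(0.958) = 83.1%.

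| Evaluable per arm | 30% | 40% | 50% | 60% | 70% |
|---|---|---|---|---|---|
| 105 | 84.6 | 83.1 | 84.6 | 89.1 | 95.7 |
| 88 | 77.8 | 76.0 | 77.8 | 83.1 | 91.9 |
| 147 | 94.2 | 93.3 | 94.2 | 96.6 | 99.2 |

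With 105 or 88 evaluable, power is below 90% at four of the five starting proportions.

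**Step 5. Joint power if both are required**, assuming the same starting proportion and effect on each outcome. At correlation 0 it is the square of the single-outcome power (0.831² = 69.0%). The ranges run from correlation 0 to 0.8.

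| Evaluable per arm | 40% vs 60% | 70% vs 90% |
|---|---|---|
| 105 | 69–77% | 91.6–93.5% |
| 88 | 58–68% | 84.5–88.2% |
| 147 | 87–90% | about 98–99% |

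**The case against.** The best defence is that the hypothesis joins the two attitudes with a conjunction. Read as a requirement for both, the unadjusted 0.05 is correct. That reading is open, but an aim is not a decision rule, and it carries the joint-power cost in Step 5. The slash in the sizing section might instead mean one combined attitude. However, sections (ii) and (iii.1) both use the plural, and no composite is defined.

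Several stronger readings are tempting, and the documents do not support them.

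- **A reader might infer that the trial's error rate is near 10%.** That needs an either-outcome rule, both nulls true and independent tests. It also counts false claims in both directions. Counting only false claims of improvement, the rate is 4.9%, 4.5% or 3.9% at the three correlations, against 2.5% for one outcome on that footing.
- **A reader might multiply two outcomes by three visits.** The plan follows participants "for 9 months to observe the effectiveness of the intervention on improving the primary outcomes, i.e., attitude to vaccination and SARS-CoV-2 testing". Month 9 is strongly implied, so six competing primary tests should not be read into it.
- **A reader might say that the plan is silent on scale, or that its primary model is wrong.** It is not silent: a proportion in one section conflicts with scores in another. The Cox model is assigned to binary outcomes and is not tied to attitude; actual uptake of testing, a secondary outcome, is a natural candidate. Its mismatch with the two-proportion sizing matters only if attitude is analysed as binary.
- **A reader might blame the single-outcome shortfall on having two outcomes.** It comes from averaging 222 and 364 and from the expected loss, and would exist with one outcome.

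Intention-to-treat does not by itself restore 147 evaluable per arm, because no handling of missing values is given. It is fair to show 147 as the upper bound.

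**Conclusion.** The point stands on two grounds.

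1. Two primary outcomes are tested at p<0.05 with no success rule and no error control across them. The inflation, to 7.8–9.75% two-sided, is conditional on an either-outcome claim. Under a both-required rule there is none, and the consequence is lower power for trial success.
2. The 90% power does not hold at 294 once the planned loss occurs, except at a starting proportion of 70%. At the least favourable proportion, 40%, single-outcome power is 83.1% or 76.0%, depending on how the 40% loss is applied.

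The error figures rest on assumed correlations. The power figures assume a binary outcome, a 20-point effect and, for 105 and 88, no primary-outcome data from lost participants. They do not apply if attitude is analysed as a continuous score. The conflict over scale must be settled because it decides which test and which power statement apply. This should be corrected, but it does not call the design into question.

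**What to change.** 1. **State the success rule before the data are seen.** Either outcome may be claimed, with two-sided 0.05 controlled by Holm or by a fixed sequence in a pre-chosen order; or both are required, with no alpha adjustment.
2. **Choose one scale for attitude** and use a month-9 between-arm comparison that matches it: a logistic model or difference in proportions if binary, a baseline-adjusted linear model if a score.
3. **Restate the power** on one evaluable-sample basis, single-outcome and, if both are required, joint. Do not attribute 90% to the trial as a whole.

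**Cost.** Wording only, with no extra enrolment. A fixed sequence leaves the first outcome's power intact but allows no claim on the second if the first fails. Holm costs some per-outcome power (simulated, binary outcome, correlations 0 to 0.8):

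| Evaluable per arm | Case | Unadjusted | Holm, both effects real | Holm, only one real |
|---|---|---|---|---|
| 105 | 40% vs 60% | 83.1% | 79.1–81.0% | about 75% |
| 105 | 70% vs 90% | 95.7% | 94.4–95.4% | about 92.5% |
| 88 | 40% vs 60% | 76.0% | 71.0–72.8% | about 66.5% |
| 88 | 70% vs 90% | 91.9% | 89.7–91.2% | about 87% |

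A both-required rule costs the joint power shown in Step 5.
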